5.5.3 MRI sub-study outcomes measures

Assessment of length and depth of meniscal tears will be performed by a radiologist using MRI at baseline and 26 weeks after surgery. The radiologist will be blinded to the patients' study allocation. The following standard grading system will be used to describe abnormal intrameniscal signals: Grade 1 – the signal is oval or globular in appearance and does not communicate with any meniscal surface; Grade 2 – the signal is a more linear but, similarly, does not communicate with the articular surfaces; Grade 3 - the signal, located within the meniscus, is linear and should communicate with either the superior or the inferior articular surfaces. Grade 1 and 2 signals are consistent with intrasubstance myxoid degeneration, whereas a Grade 3 signal is consistent with a tear. Tear patterns will be classified as longitudinal (located anywhere along the meniscus), horizontal (begins at the inner margin of the meniscus and extends towards the capsule), radial (begins at the inner margin and extends towards the capsule) or flap (either a vertical flap tear or a horizontal flap tear). By comparing the follow-up MR images with the baseline images, the presence or absence of a reduction in length and depth of the lesion can be identified. The occurrence of a new lesion with respect to baseline will be considered as a deterioration/recurrence and recorded as an adverse event. Reductions in the length and depth of the meniscal tear subsequent to baseline, assessed radiologically, were measured in relation to the index tear evaluated at baseline.

6. SUBJECTS

6.1 Anticipated number of research subjects

The sample size calculation does take into account a 10% patient attrition rate (withdrawal and loss to follow-up), since this involves a study with multiple time points for data collection up to 26 weeks. Patients will be recruited from the adult population routinely seen by the evaluating clinical staff members. The primary outcome measure is based on knee/leg (ie wound site) pain experienced 7-days post-surgery based on the VDS pain scale (with leg at rest). The hypothetical difference in pain perception, based on a previous publication involving meniscal repair and Viscoseal, is 15mm on a 100 mm scale which equates to a significant 'minimally clinically important difference' for pain (Kelly 2001; Lee et al 2003; Tashjian et al 2009).

The non-parametric two-sided Mann-Whitney u-test is applied because the data is ordinal; 80% power and 5% significance is also applied. A priori power calculations using GPower 3.1 software, result in the following sample size summarized in Table 3.

It involves a minimum total of **52 participants**, who undergo meniscal repair surgery. Randomised 1:1, therefore 26 patients per arm.

Table 3, Sample size calculation

	Mean pain score (mm) at 7 days post-op~	Standard Deviation (hypothetical)
Viscoseal	28	20
Standard care	43	20

IRAS ref 272362 Page **14** of **30**

	Power beta of 80%, Alpha p-value of 0.05, Effect size 0.75			
	Sample size required without any drop-out: 48 samples.			
	Sample size with 10% attrition rate included: 52			
	Total of 52 patients:			
	26 Patients to receive standard care			
	26 Patient to receive Viscoseal			
~Based on Thein et al. 2	010			

For the MRI imaging sub-study a total of 24 patients will be recruited, 12 controls and and 12 viscoseal patients. This is in line with guidelines on pilot studies [25].

The CONSORT guidelines require a statement on the number of patients assessed for eligibility (Schulz, Altman & Moher 2010). The number of patients screened but who did not meet the inclusion criteria or who declined to participate will be recorded, as will any patients who are lost to follow-up (Appendix 3).

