8.2 Primary outcome statistics

To determine the level of operation-site related pain – at rest - experienced at day 7 post-operation (plus day 2, day 14, week 12 and week 26) and to compare the average pain scores of patients in the control and Viscoseal arm respectively, through administration of 100 mm visual descriptor scale (VDS) for pain. To compare the groups, the Mann-Whitney U-test will be applied.

The study is powered to detect the established minimal clinically important difference (MCID) of 15 mm on a 100 mm VDS pain.

In addition, VDS scale will be used for pain upon walking.

To avoid relying on one outcome measure related to pain, at 7 and 14 days post-surgery pain perception will also be measured using the short form McGill pain questionnaire. Again, to compare groups the Mann-Whitney U-test will be applied.

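### The sample size of 48 does not follow from the stated two-sided Mann-Whitney test; it matches a one-sided calculation, and two-sided power for 15 mm is about 69–74%, not 80%

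*Protocol*

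**What the plan says.** Section 6.1 of the protocol fixes every input to the calculation. On the test and error rates it says: "The non-parametric two-sided Mann-Whitney u-test is applied because the data is ordinal; 80% power and 5% significance is also applied". Table 3 gives mean day-7 pain of 28 mm (Viscoseal) and 43 mm (standard care), with a hypothetical SD of 20 mm in each arm, and summarises the settings as "Power beta of 80%, Alpha p-value of 0.05, Effect size 0.75". The software named is G*Power 3.1; the tails setting and parent distribution are not reported.

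The results in Table 3 are "Sample size required without any drop-out: 48 samples" and "Sample size with 10% attrition rate included: 52", the latter split 26 and 26.

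Section 8.2 confirms the test for the primary outcome ("To compare the groups, the Mann-Whitney U-test will be applied") and asserts: "The study is powered to detect the established minimal clinically important difference (MCID) of 15 mm on a 100 mm VDS pain". Section 5.5.1 makes the same claim. The protocol does not mention a one-sided test anywhere.

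**The concern.** An effect size of 0.75 at two-sided 5% and 80% power needs close to 30 per arm under most standard methods, so 24 per arm looks too small. The figure is about what a one-sided test would require.

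This calculation is the only justification for the size of an efficacy trial. If the true two-sided power is nearer 70%, the risk of missing a real 15 mm benefit is about 30% rather than the stated 20%. A null result could then be taken as stronger evidence against a worthwhile effect than it is. The mismatch also leaves room for someone to settle it after the data are in by calling the test one-sided. The text should rule that out beforehand.

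**Working it through.** **Inputs (section 6.1 and Table 3).** Difference 43 − 28 = 15 mm; SD 20 mm; d = 15/20 = 0.75; alpha 0.05, two-sided; power 80%; Mann-Whitney test; 1:1 allocation; attrition 10%.

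**Method.** The Mann-Whitney test is handled through its asymptotic relative efficiency (ARE) to the t-test. With n per arm:

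- effective size m = n × ARE, where ARE = 3/π = 0.955 for a normal parent
- degrees of freedom = 2m − 2
- noncentrality = d × √(m/2)
- power = probability that a noncentral t variate with these values exceeds the critical t (plus the lower tail if two-sided).

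**Step 1: reproduce 48.** For n = 24, m = 24 × 0.955 = 22.92, df = 43.8 and noncentrality = 0.75 × √(22.92/2) = 2.539.

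- One-sided 5%: critical t = 1.680, power 80.4%. At 23 per arm the power is 78.8%, so 24 per arm (48) is the smallest size that reaches 80%. This matches the plan exactly.
- Two-sided 5%: critical t = 2.016, power 70.0%.

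**Step 2: the size that the stated test needs.** Two-sided 5%, normal parent: 30 per arm gives 79.6% and 31 per arm gives 81.0%, so 62 evaluable. The protocol does not state a parent distribution, so the alternatives were tried as well:

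| Two-sided method | Total N for 80% | Power at 24/arm | Power at 26/arm |
|---|---|---|---|
| Mann-Whitney, normal parent | 62 | 70.0% | 73.5% |
| Mann-Whitney, minimum ARE (0.864) | 68 | 65.4% | 69.0% |
| Mann-Whitney, logistic parent | 54 | 76.1% | 79.5% |
| Mann-Whitney, Laplace parent | 40 | 88.1% | 90.5% |
| t-test | 58 | 72.0% | 75.6% |

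The simple normal approximation to the t-test gives 56, and Noether's formula for the Mann-Whitney test gives about 64. No two-sided method returns 48.

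**Step 3: attrition.** 48/0.9 = 53.3, so 54 with equal arms. Conversely, 52 × 0.9 = 46.8 evaluable, or 23.4 per arm, which is below 48. Multiplying up instead, 48 × 1.1 = 52.8, also rounds up past 52.

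**Step 4: what the trial achieves** (two-sided 5%, normal parent, SD 20).

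| Evaluable per arm | Power for 15 mm | Difference detectable with 80% power |
|---|---|---|
| 23.4 (52 less 10%) | 68.8% | 17.2 mm |
| 24 (the plan's 48) | 70.0% | 16.9 mm |
| 26 (no loss) | 73.5% | 16.2 mm |

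**Step 5: simulation check.** With 40,000 simulated trials per setting, two-sided Mann-Whitney power on normal data was 69.5% at 24 per arm and 72.6% at 26. With scores rounded and clipped to 0–100 mm it was 68.7% and 73.1%. A separate run of 20,000 trials with bounded beta-distributed scores gave 72.2% at 24 per arm. The same normal-data simulation gave 79.8% for a one-sided test at 24 per arm.

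**The case against.** The strongest objections concern precision rather than the core arithmetic.

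- **The cause is inferred.** The G*Power settings are not printed, so a one-sided run is deduced from an exact match. That caveat stands. It does not affect the discrepancy, since no two-sided option tried gives 48.
- **The parent distribution is not stated.** The 69–74% range assumes a normal parent. A logistic parent gives 76–79% at 24 to 26 per arm, which is milder but still under 80%. A Laplace parent exceeds 80%, but it would have called for 40 patients, so it cannot explain 48.
- **The SD is hypothetical.** Two-sided power of 80% for 15 mm would be reached if the SD were about 17.7 mm (24 per arm) or 18.5 mm (26 per arm). This is true, but the plan's own value is 20 mm, and the question is whether its figures agree with each other.
- **Attrition at day 7 may be below 10%.** Section 6.1 ties the 10% to follow-up over 26 weeks, whereas the primary endpoint is at day 7. The top of the range may therefore be nearer the truth, with a miss rate of about 26% rather than 31%. Even with no loss at all, power is 73.5%.
- **The attrition shortfall is small.** It is: 52 against 54 is one patient per arm, and 23.4 against 24 per arm costs about one percentage point of power.

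**Conclusion.** The concern holds. The stated sample size is inconsistent with the stated two-sided test, and the claim in sections 5.5.1 and 8.2 that the trial is powered for 15 mm is wrong as written. On the plan's own inputs (d = 0.75, SD 20 mm, two-sided 5%) and a normal parent, power is 69% to 74% depending on losses. The type II error is therefore 26% to 31% against the stated 20%, and the difference detectable with 80% power is 16.2 to 17.2 mm. That a one-sided setting was used is a well-supported inference, not a documented fact. The attrition error is real but secondary. Because this is the headline power statement for the primary endpoint, it must be corrected.

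**What to change.** Keep the two-sided 5% Mann-Whitney test and say so unambiguously in section 8.2 as well as 6.1. Then:

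1. In section 6.1 and Table 3, report the G*Power settings used (tails and parent distribution) and replace the 80% claim. Suggested wording: with 52 randomised and 10% attrition (about 46 to 47 evaluable), a two-sided 5% Mann-Whitney test has about 69% power for a 15 mm difference at SD 20 mm, assuming a normal parent, or 80% power for about 17 mm; with no losses these become about 74% and 16 mm.
2. Record that 80% two-sided power for 15 mm under the same assumptions would need 62 evaluable patients. Since 62/0.9 = 68.9, that is 69 randomised, or 70 with equal arms.
3. Correct the attrition line: 52 × 0.9 = 46.8, and 48 evaluable would have needed 54 randomised.
4. Bring the power statements in sections 5.5.1 and 8.2 into line.

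The cost is protocol wording and a less favourable stated power. Restating it needs no additional patients. The change discloses the shortfall but does not remove it; removing it would mean recruiting towards the larger number.

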5.5 Outcome measures

5.5.1 **Primary outcome measures**

To determine the level of index leg related pain experienced at day 7 post-operation and to compare the average pain scores of patients in the control and Viscoseal arm respectively, through administration of 100 mm visual descriptor scale (VDS) for pain at rest.

The study is powered to detect the established minimal clinically important difference (MCID) of 15 mm on a 100 mm VDS pain.

5.5.2 **Secondary outcome measures**

All the outcome measures are summarised in Table 2.

Table 2. Overview of measurements

Weeks	-12 weeks to day of surgery	48 hours	7 days*	14 days*	12 weeks#	26 weeks~
VDS pain scale for knee (at rest)	Х	Х	Х	Х	Х	Х
VDS pain scale for knee (walking)	Χ				Х	Χ
McGill pain questionnaire (at rest)	Х	X	X	Х		
Limb girth measurement (index leg)	X			Х	Х	
Lysholm scale	Χ				Χ	X
WOMET tool	Χ				Χ	Χ
Use of analgesics / anti- inflammatories	Х	X	Χ	Х	X	X
Patient satisfaction questionnaire re surgery						Χ
MRI scan (sub-study; not all participants)						Х

^{*} Allowed to be up to 2 days early or late

IRAS ref 272362 Page **13** of **30**

[#] Allowed to be up to 2 weeks early or late

[~] Allowed to be up to 4 weeks early or late

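### The planned 48 evaluable patients do not follow from the stated two-sided Mann-Whitney test; power for 15 mm is about 70%, not 80%

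*Protocol*

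**What the plan says.** The sample size rationale is in Protocol section 6.1 and Table 3. The text fixes the test, its sidedness, the significance level and the power: "The non-parametric two-sided Mann-Whitney u-test is applied because the data is ordinal; 80% power and 5% significance is also applied". It names GPower 3.1 as the software. It does not name the parent distribution assumed for the Mann-Whitney calculation.

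Table 3 gives means of 28 mm (Viscoseal) and 43 mm (standard care) at day 7 and an SD of 20 mm in each arm, which it labels hypothetical. It then states "Power beta of 80%, Alpha p-value of 0.05, Effect size 0.75" and "Sample size required without any drop-out: 48 samples". Attrition of 10% brings the total to 52, or 26 per arm.

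Sections 5.5.1 and 8.2 both rest on this calculation: "The study is powered to detect the established minimal clinically important difference (MCID) of 15 mm on a 100 mm VDS pain". The protocol nowhere mentions a one-sided test.

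**The concern.** An effect size of 0.75 with 24 per arm looks too small for 80% power in a two-sided rank test. Even the two-sided t-test needs more patients than that, and under a normal parent the Mann-Whitney test is slightly less efficient than the t-test.

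The figure concerns the primary comparison and supports the claim that the trial can detect the minimal clinically important difference. If the power is overstated, a true 15 mm benefit will be missed more often than declared, and a non-significant result will look like stronger evidence against a 15 mm effect than it is.

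The error lies in the 48 itself, before any allowance for attrition.

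**Working it through.** **Inputs (section 6.1 and Table 3).** Difference 43 − 28 = 15 mm; SD 20 mm; effect size d = 15/20 = 0.75, which agrees with the table; alpha 0.05; target power 80%; allocation 1:1.

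**Assumption.** A normal parent distribution, because the protocol names none. Its asymptotic relative efficiency (ARE) against the t-test is 3/π = 0.955.

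**Formula.** For n patients per arm, take m = n × ARE, df = 2m − 2 and noncentrality δ = d × √(m/2). Power is the probability that a noncentral t(df, δ) variable exceeds the critical value, plus the opposite tail for a two-sided test.

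**Step 1: reproduce the printed 48.** With n = 24: m = 24 × 0.955 = 22.92, df = 43.8, δ = 0.75 × √11.46 = 2.539.

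- One-sided 5% (critical t = 1.680): power 80.4%. At 23 per arm it is 78.8%. The smallest sufficient number is therefore 24 per arm, total **48**, an exact match.
- Two-sided 5% (critical t = 2.016): power **69.9%**.

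**Step 2: number needed for the test as stated.** Two-sided, 30 per arm gives 79.6% and 31 per arm gives 81.0%. The requirement is 31 per arm, total **62**.

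**Step 3: does another method give 48 with a two-sided test?**

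| Two-sided method | Total N for 80% | Power at 48 |
|---|---|---|
| Minimum ARE (0.864) | 68 | 65.4% |
| Noether formula | about 64 | not computed |
| Normal parent | 62 | 69.9% |
| t-test, or uniform parent (ARE 1) | 58 | 72.0% |
| Plain normal approximation | 56 | 73.8% |
| Logistic parent | 54 | 76.1% |
| Laplace parent | 40 | 88.1% |

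None gives 48. Only the heavy-tailed Laplace parent exceeds 80% at 48, and its own answer would have been 40.

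**Step 4: power at the numbers the trial may have (two-sided, normal parent).**

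- 48 evaluable (24 per arm): 69.9%, so a type II error of 30.1%, about 1.5 times the declared 20%.
- All 52 evaluable (26 per arm): 73.5%.
- 10% loss from 52, i.e. 52 × 0.9 = 46.8 or about 47 evaluable: 68.8%.

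**Step 5: what 48 evaluable can detect.** Solving for 80% two-sided power at 24 per arm gives d = 0.846. That is 0.846 × 20 = 16.9 mm at SD 20, or 15/0.846 = an SD of 17.7 mm for a 15 mm difference.

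**Step 6: simulation.** Mann-Whitney tests on simulated data at 24 per arm (28 v 43 mm, SD 20) gave two-sided power of about 70% for normal data, about 70% with values clipped to 0–100, and 73% for beta-distributed data with the same means and SD. At 31 per arm the normal simulation gave 80.6%. The one-sided simulation at 24 per arm gave 80.1%.

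**The case against.** The strongest reply has four parts.

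- **The one-sided origin is inferred.** No software output is shown and no parent distribution is named. This stands as a caution about cause. It does not touch the error, because the stated two-sided inputs fail to give 48 under every method tried.
- **70% is one point in a range.** This is fair. It assumes a normal parent and 48 evaluable. Because 52 are randomised and the endpoint is at day 7, while the 10% attrition is justified by follow-up to 26 weeks, actual loss could be smaller and power nearer 73.5%. The normal-parent range is about 69% to 74%, all below 80%. The logistic parent also stays below at 52 evaluable (79.4%).
- **The SD is hypothetical.** A smaller one would restore power: about 17.7 mm at 48 evaluable, or about 18.5 mm at 52. True, but nothing in the protocol supports a value below 20, and the printed calculation uses 20.
- **The sponsor could raise the sample size instead.** It could: 62/0.9 gives 69, so 70 for equal arms. That is a choice about resources. An honest statement of power at 52 is enough to correct the document.

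It is also true that sections 5.5.1 and 8.2 give no percentage. They repeat the consequence of the error in 6.1 and are not separate errors.

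**Conclusion.** The concern holds. The protocol's stated test, alpha, power and effect size are incompatible with its stated 48. The two-sided Mann-Whitney test needs 62 evaluable under a normal parent, and power for 15 mm at 48 is about 70%.

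This rests on the protocol's own means and SD and on the normal-parent assumption. Of the alternatives tried, only a Laplace parent would bring power at 48 to 80%, and it would not produce 48 as the required number. The one-sided calculation is the likely source, since it matches exactly, but the conclusion does not depend on it. Because the power of the primary test is wrong as printed and the claim recurs in 5.5.1 and 8.2, it must be corrected.

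**What to change.** - **Section 6.1 and Table 3:** keep the two-sided 5% test and 52 patients, and restate the power. Suggested text: *With 48 evaluable patients, the two-sided Mann-Whitney test has about 70% power for a difference of 15 mm (SD 20 mm, normal parent), and about 74% if all 52 are evaluable. With 48 evaluable, 80% power applies to a difference of about 17 mm.* Name the parent distribution used.
- **Sections 5.5.1 and 8.2:** replace the sentence that the study is powered for 15 mm with wording that matches 6.1.
- **Interpretation:** add that a non-significant result does not by itself exclude a 15 mm effect.
- **Do not** change the final test to one-sided to fit the printed number. That would relax the declared error rate after the fact.

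The cost is protocol wording only. No extra patients are needed, and the stated power becomes less favourable.

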6.1.1 Randomisation

Following written consent, participants are allocated at random to the control or Viscoseal intervention group, using a randomised sequence from the freeware randomisation programme, see https://www.randomizer.org/.

To take into account that not all patients will consent to taking part in the MRI sub-study, two randomisation sequences will be produced. One for patients who consent to both trial and MRI sub-study and one for patient who only consent to the main trial. This means:

- 24 patients for main trial + MRI sub-study (12 control and 12 Viscoseal)
- 28 patients for main trial only (14 control and 14 Viscoseal).

In this manner both control and Viscoseal arms are equally represented in the MRI sub-study and the remaining patients for the main trial are also equally distributed amongst the two study arms.

If one of the two randomisation blocks is full, then only the remaining block will be recruited to. However, North Cumbria Integrated Care is the only NHS Trust to conduct the MRI-substudy.

Sequential envelopes with each next randomisation allocation (for each randomisation block) will be used to achieve concealment and these will be kept in the research department. The researcher or regular healthcare professional for the participant in question can e-mail ([contact]) or phone the R&D Dept ([name]) to determine which treatment the next participant has been allocated to.

6.2 Eligibility criteria

IRAS ref 272362 Page **15** of **30**

6.2.1 Inclusion criteria

- Patients has mechanical symptoms and pain and MRI evidence of meniscal tear, amenable to surgical repair
- Meniscal surgical repair of the knee for meniscal tear grade III
- Proficient in English (reading and writing, due to surveys being sent electronically)
- Adult patients aged > 18 years and < 60 years
- Mental capacity to give written informed consent and follow trial measurements

6.2.2 Exclusion criteria

- Under the age of 18 years or over 59 years
- Unable to fully understand the consent process and provide informed consent due to either language barriers or mental capacity
- Menisectomy
- Previous surgery on affected knee
- Progressive joint disease (osteoarthritis of the affected knee, Kellgren & Lawrence grade 3 or above),
- Accompanying hip osteoarthritis of sufficient severity to interfere with the functional assessment of the knee;
- Known or suspected infection of the affected joint;
- Painful knee conditions other than osteoarthritis, such as rheumatoid diseases (RA, gout);
- Other joint diseases or previous management of the operated knee within the last year that might interfere with the assessment of the meniscal repair
- Limited life expectancy, i.e. undergoing palliative care
- Any condition that is associated with excessive bleeding, coagulation abnormalities or any other significant haematological condition (e.g. Factor V Leiden, haemophilia).
- Patients who are participating in another interventional research study involving an investigational product related to the knee surgery procedure and its aftercare.
- The patient has concurrent (medical) conditions that in the opinion of the investigator may compromise patient safety or study objectives.
- BMI > 35 (Patients with BMI>35 are not suitable for day surgery and their pathway of care would differ significantly from the majority group BMI<35 hence the restriction)
- Known hypersensitivity to hyaluronic acid, other constituents of Viscoseal, marcaine, codydramol
- Any auto-immune disease that affects the limbs, such as rheumatoid arthritis, treated with immune-modulating drugs.
- Inflammatory arthropathy.
- Co-existing condition that significantly impacts on usual daily activities (including, but not limited to, lower limb amputation, cancer, neurodegenerative disease, or other condition that leaves patient invalid or to use a wheelchair) as assessed by recruiting clinician.
- Contraindications for MRI diagnostics (see https://radiology.ucsf.edu/patient-care/patient-safety/mri/absolute-contraindications) since qualifying meniscal injury pre-surgery needs to be demonstrated by MRI.

IRAS ref 272362 Page **16** of **30**

